- c. **Statistical Analysis**: The Fisher Exact test will be use to compare 28day mortality in the two groups. Statistical significance will be determined according to the interim analyses procedures describe below. If adjustment for pre-defined confounders is needed, we will use the above-defined method for categorical, binary variables.
- d. **Interim analyses:** We planned 5 analyses (4 interim, 1 final), equally spaced, using the O'Brien-Fleming method to calculate two-sided boundaries, assuming a 95% confidence and 80% power. All patients entered in each interim analyses will have complete data on 28-day mortality (i.e., the analyses will be conducted only once the 28-day observation period for all survivors have been completed).
- e. **Sample Size and Power:** This is a Phase 2 trial and is powered to detect large (17 to 19 percent-point) differences in mortality between the two groups.

Primary endpoint power calculations: 28-day mortality

Assumptions: 80% power, 95% confidence, 2-tailed test, P2=mortality in control group, P1=mortality in experimental group; 3 equally spaced data analyses, as determined by number of patients enrolled (2 interim when 1/3 and 2/3 of the predicted sample or 20 and 40 patients were enrolled, and a final when 60 to 75 patients were enrolled), using the O'Brien-Fleming method; control group 30-day mortality of 26% (based on control arm of ROC HS trial⁶⁷) and three attrition rates (0, 10%, 20%)

	Power	N1	N2	Alpha	Beta	P1	P2	Difference	Attrition Rate
	0.800000	60	60	0.050000	0.200000	0.07	0.26	0.19	20%
	0.800000	68	68	0.050000	0.200000	0.08	0.26	0.18	10%
L	0.800000	75	75	0.050000	0.200000	0.09	0.26	0.17	0%

Sample size of 60 and 60 achieves 80% power to detect a difference of 0.19 between the group proportions at a significance level (alpha) of 0.05 using a two-sided test. These results assume that 3 sequential tests are made using the O'Brien-Fleming spending function to determine the test boundaries, as seen below.

Boundaries (Bndry) for data looks Details when Spending = O'Brien-Fleming, N1 = 60, N2 =60, P1 = 0.07, P2 = 0.26 Lower Upper Nominal Inc Total Inc Total

^{*} Although the hypothesis is worded as "higher", all tests will be two-tailed to control for differences in either direction (higher or lower than the other group).

Look	Bndry	Bndry	Alpha	Alpha	Alpha	Power	Power
1	-3.71030	3.71030	0.000207	0.000207	0.000207	0.018650	0.018650
2	-2.51142	2.51142	0.012025	0.011890	0.012097	0.398801	0.417451

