3	-1.99302	1.99302	0.046259	0.037903	0.050000	0.382549	0.800000
Details whe	en Spending = C)'Brien-Flem	ning, N1 = 68	, N2 =68, P1	= 0.08, P2 =	0.26	
	Lower	Upper	Nominal	Inc	Total	Inc	Total
Look	Bndry	Bndry	Alpha	Alpha	Alpha	Power	Power
1	-3.71030	3.71030	0.000207	0.000207	0.000207	0.018650	0.018650
2	-2.51142	2.51142	0.012025	0.011890	0.012097	0.398801	0.417451
3	-1.99302	1.99302	0.046259	0.037903	0.050000	0.382549	0.800000
Details whe	en Spending = C)'Brien-Flem	ning, N1 = 75	, N2 =75, P1	= 0.09, P2 =	0.26	
	Lower	Upper	Nominal	Inc	Total	Inc	Total
Look	Bndry	Bndry	Alpha	Alpha	Alpha	Power	Power
1	-3.71030	3.71030	0.000207	0.000207	0.000207	0.018650	0.018650
2	-2.51142	2.51142	0.012025	0.011890	0.012097	0.398801	0.417451
3	-1.99302	1.99302	0.046259	0.037903	0.050000	0.382549	0.800000

Addendum Nov 16, 2016

At the second interim analyses, we had enrolled 100 patients (2/3 of the 150 total sample size), of whom 88 (12% attrition rate) patients were eligible for analysis (please, see Interim Analyses report for details). This attrition rate was similar to the lowest anticipated attrition rate (see first table above). Yet we noticed several important differences regarding the assumptions used to estimate the sample size. In brief, the cohort enrolled based on the entry criteria (field systolic blood pressure, SBP<70mmHg or SBP <90mmHg AND heart rate>108bpm) was less severely injured than anticipated (as measured by base deficit, INR and TEG G) and had lower mortality than anticipated.

Variable	Anticipated (sample size/power analyses assumptions)	COMBAT group A	COMBAT group B
INR	1.47	1.32	1.38
INR>1.5	24% to 36% *	18%	16%
Base deficit (mEq/L)	5.15	11.2	9.2
TEG G dynes/cm ²	4.9	7.3	7.5
Mortality	26%	12%	13%

* {MacLeod, 2003 #1415;Maegele, 2007 #905;Niles, 2008 #4410}

In addition, a slightly lower proportion of patients required transfusions (55% of group A, 61% of group B) compared to our anticipated proportion based on trauma registry data encompassing the period of January 2009-December 2011 (3 years) and excluding patients who died within 10 minutes of arriving at ED (64%).

Although we enrolled a cohort with less physiologic and coagulation derangement than anticipated, which decreased our statistical power to detect differences in the primary and secondary outcomes, we detected some promising trends, as follows:

[figure not shown]

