There are several explanations for the differences in the expected and observed values. First, for the most common injury mechanisms, the case-fatality rate is decreasing in our trauma center ([name] et al. JAMA, 2016). Second, the wide use of TEG-guided hemostatic resuscitation in our institution has been associated with a dramatic decrease in post-injury mortality (Gonzalez, Ann Surg, 2016). In addition, our findings are not isolated. A recent multicenter RCT (Connelly et al., JAMA Surgery, 2016) also noted that the patients enrolled were less severely injured than anticipated based on previous experiences. Given the time required to establish such intense trials, usually one to two years, the assumptions used in the calculation of the sample size can understandably become outdated. This has prompted proposals of alternative designs for RCTs, such as adaptive and Bayesian RCTs as recently described by an NIH-funded workshop (Coffey et al. Clinical trials, 2012).

Based on the explanations above, we propose a continuation of the trial to increase sample size and make it adequate to detect differences in the proposed outcomes (mortality, admission acidosis and coagulation, hemorrhage as well as requirement for blood products), as follows:

Hypothesis for primary endpoint above: 28-day mortality will be significantly higher in control patients compared to experimental patients.

With 80% power, 95% confidence and assuming 12% mortality rate in the control group (based on the second interim analyses data), with 5 interim analyses (4 interim and 1 final, of which 3 already occurred), we will require 112 patients in each group (assuming the attrition rate observed in this RCT of 12%) to detect a difference of 10 percent points. This results in a total of 224 patients, which corresponds to an increase of 74 patients over the current sample size of 150 patients. See below the significance level for the 5 analyses.

Spending = O'Brien-Fleming, N1 = 112, N2 =112, P1 = 0.12, P2 = 0.02, Continuity Correction.

		Lower	Upper	Nominal	Inc	Total	Inc	Total
Look	Time	Bndry	Bndry	Alpha	Alpha	Alpha	Power	Power
1	0.20	-4.87688	4.87688	0.000	0.000	0.000	0.00015	0.000
2	0.40	-3.35695	3.35695	0.001	0.001	0.001	0.05885	0.059
3	0.60	-2.68026	2.68026	0.007	0.007	0.008	0.25750	0.317
4	0.80	-2.28979	2.28979	0.022	0.017	0.024	0.28890	0.605
5	1.00	-2.03100	2.03100	0.042	0.026	0.050	0.19460	0.800

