Based on the interim analyses, a proposed new sample size is: with 80% power, 95% confidence and assuming mean admission INR = 1.32 with standard deviation of 0.5 in the control group (based on the second interim analyses data), with 5 interim analyses (4 interim and 1 final, of which 3 already occurred), we will require 112 patients in each group (assuming the attrition rate observed in this RCT of 12%) to detect a difference of 0.19 (from 1.32 to 1.13) between the two mean INRs. This results in a total of 224, which corresponds to an increase of 74 patients over the current sample size of 150 patients.

- e. **Hypothesis 2.2:** The incidence of admission coagulopathy as measured by INR>1.5 will be significantly higher[§] in control patients compared to experimental group patients.
- f. Statistical test 2.2: Logistic regression will be used to compare the incidence of admission coagulopathy between the two groups. Statistical significance will be determined according to the interim analyses procedures describe below. If adjustment for pre-defined confounders is needed, we will use the above-defined method for categorical, binary variables.
- g. **Sample size and Power calculations:** this is a Phase 2 trial, powered to detect differences in this outcome as follows:

Assump final), u	Power calculations: Admission coagulopathy Assumptions 1 : 80% power, 95% confidence, 2-tailed test, 3 equally spaced data analyses (2 interim, 1 final), using the O'Brien-Fleming method; control group admission coagulopathy incidence 24%, 28% and 36% (based on ^{11, 86, 87}).										
Power		N1	N2	Alpha	Beta	P1	P2	Difference	Attı	rition Rate	
0.8000	000	60	60	0.050000	0.200000	0.06	0.24	0.18	20%	, D	
0.8000	000	68	68	0.050000	0.200000	0.07	0.24	0.17	10%	, D	
0.8000	000	75	75	0.050000	0.200000	0.07	0.24	0.17	0		
0.8000	000	60	60	0.050000	0.200000	0.08	0.28	0.18	20%	6	
0.8000	000	68	68	0.050000	0.200000	0.09	0.28	0.17	10%	6	
0.8000	000	75	75	0.050000	0.200000	0.10	0.28	0.16	0		
0.8000	000	60	60	0.050000	0.200000	0.14	0.36	0.22	20%	6	
0.8000	000	68	68	0.050000	0.200000	0.15	0.36	0.21	10%	6	
0.8000	000	75	75	0.050000	0.200000	0.16	0.36	0.20	0		
Sample	sizes of	f 60 an	d 60 achi	eve 80% pow	er to detect a	difference of	of 0.18 bet	ween the gro	up pro	portions at a	
significa	nce lev	el (alph	a) of 0.05	using a two-s	sided test. The	se results as	sume that i	3 sequential to	ests are	e made using	

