- 1. Assessing Phase 2 trial results for promising benefits of the therapy: Because the trial has low power for the primary endpoint and some of the secondary endpoints, it is unlikely that we can detect a statistical significant difference. Thus, it is important to pre-determine the findings that we believe will indicate promising results that must be further investigated in larger Phase 3 trials. We will specifically look at the following measures to declare that the therapy is promising:
 - a. Statistical significant difference in primary endpoint or secondary endpoints
 - b. Strong, yet not statistically significant association (e.g., p-value = 0.10 to 0.05) with improved primary and secondary endpoints. The direction

of the association must indicate therapy benefit in ALL primary and secondary endpoints. Associations indicating harm will be reviewed by the DSMB for possible early termination.

c. Exploratory analyses of variables with supporting evidence for association with improved patient outcomes with statistically significant results (respecting the boundaries determined by the interim analyses methods, and adjusted for multiple comparisons as detailed in the description of the exploratory analyses).

The DSMB will also be in charge to making recommendations regarding the promising nature of the therapy and whether Phase 3 trials are warranted.

2. Interrupting the trial early:

The DSMB will be responsible for making a recommendation for early stopping of the trial. The DSMB will be asked to address early termination during each and every time they are activated, as described in the DSMB roles and responsibilities. In brief, the DSMB will be activated in case of a unanticipated problem, or during the interim analyses. Drs. [name] and [name] will prepare the materials for DSMB review containing:

- a. blinded results (experimental and control groups will be referred as A and B) of effectiveness of randomization, primary and secondary outcomes, as well as exploratory analyses (most especially the two subgroup analyses regarding blunt versus penetrating mechanism, presence of traumatic brain injury and Field SBP≤70mmHg versus SBP 71-90mmHg), any potential adverse events, and missing data description (to include number missing and their characteristics regarding outcomes and covariates).

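### The addendum's 80% mortality power is an unconditional figure for 112 analysed patients per arm; it does not follow from the stated 12% attrition and leaves out the look-2 result

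*Combined protocol and SAP*

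**What the plan says.** The original power table in Section IV.E lists 75, 68 and 60 per arm for attrition of 0%, 10% and 20%. The test is fixed in the same section: "The Fisher Exact test will be use to compare 28day mortality in the two groups".

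The addendum of November 16, 2016 reports look 2. One hundred patients were enrolled, "of whom 88 (12% attrition rate) patients were eligible for analysis", with mortality of 12% in group A and 13% in group B. It then proposes the larger trial. The calculation opens "With 80% power, 95% confidence and assuming 12% mortality rate in the control group (based on the second interim analyses data") and concludes: "we will require 112 patients in each group (assuming the attrition rate observed in this RCT of 12" per cent). The total of 224 is described as a figure "which corresponds to an increase of 74 patients over the current sample size of 150 patients". The accompanying table uses N1 = N2 = 112, 12% versus 2%, a continuity correction and five O'Brien-Fleming looks. Power accumulates from look 1 to 0.800. The addendum describes the looks as "with 5 interim analyses (4 interim and 1 final, of which 3 already occurred").

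Section IV.I.1 says: "Because the trial has low power for the primary endpoint and some of the secondary endpoints, it is unlikely that we can detect" a significant difference.

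On the analysis set, Section IV.D.3 requires intention to treat. Section IV.H collects vital status on everyone randomised, expects less than 2% missing, and counts unverified patients as alive.

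**The concern.** The 80% is the stated mortality basis for 74 more patients, and two things separate it from the power the extended trial could expect. First, it is unclear whether 112 is before or after attrition. Second, the addendum takes its 12% control rate from look 2 but leaves the look-2 comparison out of the power, although those 88 patients make up a large part of the final data.

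Anyone judging the extension, or later reading a non-significant mortality result, could take the trial as having had an 80% chance of detecting a 10-point reduction. Section IV.I.1 points the other way without saying which effect it has in mind.

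**Working it through.** **1. Reproduce the 80%.** Inputs from the addendum: 112 per arm, 12% versus 2%, bounds 4.877, 3.357, 2.680, 2.290 and 2.031 at information times 0.2 to 1.0.
- The bounds give total alpha 0.0500. A drift of 2.835 gives 80% power and matches every printed power increment.
- With 112 analysed per arm, power is 80.9% with the exact sequential Fisher test and 79.1-80.6% with a half-unit continuity correction (0.5/n).

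So 80% is right for 112 analysed per arm with no data yet observed.

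**2. Apply the stated attrition.**
- Original table: 75 × 0.90 = 67.5, printed as 68, and 75 × 0.80 = 60. The reduced number is what enters the power calculation.
- Addendum on the same convention: 112 × 0.88 = 98.6, about 99 per arm. The table nevertheless enters 112, and 2 × 112 = 224 is set against the planned 150.
- Power at 99 per arm: 74.2% (Fisher), 73-75% (half-unit correction).
- The INR addendum (difference 0.19, SD 0.5) shows the same pattern: 80.2% at 112 and 75.2% at 99.

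**3. Which group is control?** The documents do not say. The INR addendum is worded "assuming mean admission INR = 1.32 with standard deviation of 0.5 in the control group (based on the second interim analyses data"). Its 1.32, and the control inputs of 12% mortality, 18% with INR>1.5 and base deficit 11, match column A (1.32, 12%, 18%, 11.2) and not column B (1.38, 13%, 16%, 9.2). A as control is therefore an inference.

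**4. Which counts are possible?** Arm sizes and deaths are not given. With 88 patients, A must round to 12% and B to 13%. Nine splits do so, from 4/33 and 7/55 to 7/58 and 4/30. An even 44/44 is impossible: 5/44 = 11.4% and 6/44 = 13.6%.

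**5. Conditional power.** This is the probability of rejecting at look 3, 4 or 5 given the look-2 counts, with later deaths binomial at 12% (control) and 2% (plasma). Rejection at look k means two-sided Fisher p ≤ 2(1 − Φ(b_k)), that is 0.00736, 0.02203 and 0.04225. Each pair below is for 99 / 112 analysed per arm.

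| Look 2, A and B | A control | B control |
|---|---|---|
| 5/41, 6/47 (near-even) | 4% / 10% | 9% / 20% |
| 5/43, 6/45 (near-even) | 3% / 8% | 11% / 23% |
| 6/49, 5/39 | 7% / 18% | 5% / 12% |
| 6/50, 5/38 | 6% / 16% | 5% / 13% |
| 4/34, 7/54 (very uneven) | 1% / 4% | 20% / 36% |
| 7/57, 4/31 (very uneven) | 16% / 30% | 2% / 6% |

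**6. Why it is so low.** Take 5/43 and 6/45 with 112 per arm.
- Expected control deaths: 5 + 0.12 × 69 = 13.3, or 11.9%.
- Expected plasma deaths: 6 + 0.02 × 67 = 7.3, or 6.6%.
- The expected final difference is about 5 points, not 10. With 7 plasma deaths, 18 control deaths are needed at the final bound.
- With no further plasma death (6 in all), 16 control deaths are still needed. That means 11/69 = 16% later control mortality against the assumed 12%. Conditional power in that best case is 7-23% for near-even splits.

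**7. Look bookkeeping.** The addenda say three analyses had occurred, while those in Sections IV.E and IV.F.1 refer only to the first and second. Section IV.D.5 places the first look at one third of enrolment and also at n = 50. That fits 50/150, but 50/224 = 22%. Three-look and five-look bounds are both printed, without saying which applied at completed looks.

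**The case against.** **Attrition.** Intention to treat, under 2% missing vital status and unverified patients counted as alive would keep nearly 112 per arm in the analysis, and 80% unconditional power would then stand. This is a fair point, and 74% is not established as the true figure. But look 2 analysed 88 of 100, and un-enrolment (Section IV.J.9) or withdrawal with data destroyed (Section IV.M.1.d) may contribute. The two accounts of the analysis set conflict. The same conflict leaves open whether exactly those 88 carry forward. Without a continuity correction, 99 per arm would give 78-79%, but the addendum names a correction and the planned test is Fisher.

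**Conditional power.** The 3-10% rests on inferred arm identity, assumed counts, the Fisher test and no look-3 data. For near-even splits an uncorrected pooled z-test gives about 6-16%, and a B-value approximation about 20-32%. The narrow range is therefore uncertain, but every version is far below 80%.

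**Disclosure.** Section IV.I.2.c already gives the DSMB predicted future test statistics, and an Interim Analyses report is cited. A reader might infer that those who reviewed the extension lacked conditional information. The documents show only that the protocol text prints none. Section IV.I.1 warns of low power, the trial is Phase 2, and the extension is also justified by acidosis, coagulation and transfusion outcomes.

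**Other stronger readings.** A reader might infer that mixing bounds inflates false positives enough to need a stricter final bound. For mortality, Fisher error is about 3% either way (2.8-3.1% at 12% mortality). On the Z scale it is 4.7% with five-look bounds throughout and 5.3% with three-look bounds at looks 1-2, and the documents do not say which applied. A reader might also infer that the count of three completed looks is wrong. The documents do not show which count is wrong, and if look 3 had occurred, conditioning on look 2 would be out of date.

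**Conclusion.** The concern holds. The 80% is arithmetically correct as unconditional power for 112 analysed per arm. It does not follow from the addendum's own attrition statement if 112 is the number enrolled, in which case Fisher power is about 74%.

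Given look 2, and assuming the 88 patients stay in the final Fisher test and all later patients follow 12% versus 2%, conditional power with A as control is about 1-30% over all admissible splits and 3-10% for near-even ones. With B as control it is about 9-23% for near-even splits and at most 36% for any split.

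Confidence is high that conditional power is far below 80%, and lower for any particular range. The 80% and the low power in Section IV.I.1 can both be true for different effects, so that part is an unreconciled statement rather than a proven contradiction.

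**What to change.** - **Section IV.E addendum, stated power.** Label the 80% as unconditional for 112 analysed per arm. Say whether 112 is enrolled or analysed. If it is enrolled with 12% attrition, restate power as about 74%. Reconcile the 88 of 100 with the analysis set in Sections IV.D.3 and IV.H.
- **Conditional power.** Report it beside the 80%, from the actual arm counts and with assumptions stated. If masking requires, do this through the DSMB or the Interim Analyses report and not in the protocol text.
- **Section IV.I.1.** Name the effect size for which power is low, so that it agrees with the addendum.
- **Looks.** Reconcile the three analyses said to have occurred with the two reported, and the one-third wording in Section IV.D.5 with n = 50 of 224. State which bounds applied at each completed look. Leave the printed final bound as it is.

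The cost is wording and one calculation from data the trial already holds, with no extra patients. The downsides are a less favourable stated power and the need to control access to comparative interim data while the trial runs.

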- **3. Intent to treat analysis:** primary and secondary outcome data will be collected in all patients regardless of treatment received.⁸⁴ An "intent-to-treat" approach will be used for all primary/secondary outcome analyses, i.e., we will compare the outcomes of the two groups according to the group assignment at time of randomization, regardless of what treatment participants actually received. Phase 2 trial, this approach will allow a preliminary evaluation of the

effectiveness of the proposed treatment (in addition to the efficacy assessment), since the health care of the subjects reflects the health care available to civilian trauma. More details are given in the sections describing statistical analysis as well as the missing data prevention and treatment.⁸⁴

In addition to the "intent to treat" approach, this study design also supports that exploratory analyses assess the association between the dose of plasma received in the field and the primary/secondary outcomes, an equivalent to the estimand "Outcome Improvement in Tolerators" described by the Panel on Handling Missing Data in Clinical Trials.⁸⁴ This will provide information on possible "dose-response" patterns for Phase 3 trials.

- 4. Power analysis: Power analyses for each primary endpoint in Stage I and II were performed using Pass 11 (Hintze, J. (2011). PASS 11. NCSS, LLC. Kaysville, Utah, USA. www.ncss.com). All power analyses account for two interim analyses for a total of three sequential, equally spaced analyses, assuming attrition rates of 0%, 10%, and 20%.
- 5. Interim analyses: We planned 5 analyses (4 interim, 1 final), equally spaced, using the O'Brien-Fleming method to calculate two-sided boundaries, assuming a 95% confidence and 80% power. Spacing will be defined by number of enrolled patients. The first look at the data will be done when one third of the predicted total enrollment has been reached and all patients accrued have been observed for the total 28-day period or till death, whatever occurs earlier. The first interim analysis will be conducted when n=50, the second at n=100, the third at n=150, the fourth at n=200 and the final at end of the 5-year period of accrual.

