	Lower	Upper	Nominal	Inc	Total	Inc	Total
Look	Bndry	Bndry	Alpha	Alpha	Alpha	Power	Power
1	-3.71030	3.71030	0.000207	0.000207	0.000207	0.018650	0.018650
2	-2.51142	2.51142	0.012025	0.011890	0.012097	0.398801	0.417451
3	-1.99302	1.99302	0.046259	0.037903	0.050000	0.382549	0.800000

Addendum November 16, 2016

Using the results of the first and second interim analyses, a new calculation for the sample size demonstrates: with 80% power, 95% confidence and assuming a 14% rate of the composite outcome in the control group (based on the second interim analyses data), with 5 interim analyses (4 interim and 1 final, of which 3 already occurred), we will require 112 patients in each group (assuming the attrition rate observed in this RCT of 12%) to detect a difference of 11 percent points. This results in a total of 224 patients, which corresponds to an increase of 74 patients over the current sample size of 150 patients.

2. Secondary Objective 2: To determine if early administration of plasma in the field will improve the incidence of early postinjury coagulopathy on admission compared to the current standard of care.

Secondary Endpoint 2: Admission coagulopathy. This is an endpoint for which there is ample evidence of a strong association with mortality.^{11, 86, 87}

- a. Definition: Admission coagulopathy will be measured by the admission international normalized ratio for pro-thrombin time (INR). INR will be defined as the first INR obtained upon ED arrival. The target time point is 30 minutes after ambulance arrival to injury scene. Our institution's average time from arrival of ambulance to scene till arrival in ED is 28 minutes ⁸⁸. INR obtained more than 60 minutes from arrival of ambulance to scene will not be used as the endpoint.
- b. **Hypothesis 2.1:** Admission INR will be significantly higher[‡] in control patients compared to experimental group patients.
- c. **Statistical test 2.1:** Linear regression will be used to compare the mean admission INR of the two groups. Statistical significance will be determined according to the interim analyses procedures describe

[‡] Although the hypothesis is worded as "higher", all tests will be two-tailed to control for differences in either direction (higher or lower than the other group).

below. If adjustment for pre-defined confounders is needed, we will use the above-defined method for continuous, normally distributed variables.

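### The November 2016 addendum re-tables alpha from zero without recording the limits used at completed looks; if looks 1 and 2 used the three-look limits, nominal error is about 5.3%, not 5.0%

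*Combined protocol and SAP*

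**What the plan says.** **Three-look design.** Section IV.D.4 states: "All power analyses account for two interim analyses for a total of three sequential, equally spaced analyses". The primary-endpoint sample size section (IV.E, item e) repeats it: "These results assume that 3 sequential tests are made using the O'Brien-Fleming spending function to determine the test boundaries, as seen below". Its tables give critical values 3.71030, 2.51142 and 1.99302, with cumulative alpha 0.000207, 0.012097 and 0.050000. The largest sample is 75 per arm, 150 in total.

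**Look 2.** The addendum of 16 November 2016 in the same section places this look on that schedule: "At the second interim analyses, we had enrolled 100 patients (2/3 of the 150 total sample size". It reports 88 patients eligible for analysis and mortality of 12% in group A and 13% in group B.

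**Five-look design.** The addendum then resizes the trial: "with 5 interim analyses (4 interim and 1 final, of which 3 already occurred), we will require 112 patients in each group". The new table is headed "Spending = O'Brien-Fleming, N1 = 112, N2 =112, P1 = 0.12, P2 = 0.02, Continuity Correction". At times 0.2 to 1.0 it gives critical values 4.87688, 3.35695, 2.68026, 2.28979 and 2.03100, with cumulative alpha 0.000, 0.001, 0.008, 0.024 and 0.050.

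**Calendar and looks held.** Section IV.D.5 and item d of IV.E now say that five analyses were planned, "using the O'Brien-Fleming method to calculate two-sided boundaries, assuming a 95% confidence and 80% power". IV.D.5 sets looks at n=50, 100, 150 and 200 and a final one, but still puts the first at one third of planned enrolment. The addendum to Secondary Objective 1 (IV.F.1) draws on two looks only: "Using the results of the first and second interim analyses, a new calculation for the sample size demonstrates". It too says that three have occurred.

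**The concern.** Alpha allotted to a look that has been held cannot be returned to the budget. The three-look design had allotted 0.0121 by n=100. The addendum allots about 0.0008 to that look and builds all later limits on the smaller figure. If the early looks used the three-look limits, the printed total of 0.050 is not the error rate of the trial actually run. IV.D.5 promises early boundaries that do not inflate the overall error.

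The count of looks also matters. In the three-look design the third look, at n=150, was the final analysis and used up all of the alpha.

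The extension was decided with results by coded arm in view. The same final threshold (p about 0.042) also governs the secondary endpoints resized to 224. IV.I.1 makes statistical significance on primary or secondary endpoints one ground for calling the therapy promising.

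**Working it through.** **1. Reproducing both tables.** The O'Brien-Fleming-type spending function with alpha/2 per side is A(t) = 4[1 − Φ(2.2414/√t)], where 2.2414 is the 98.75% normal quantile.

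- t = 1/3, 2/3, 1 gives 0.000207, 0.012097, 0.050000, as in the three-look table.
- t = 0.2, 0.4, 0.6, 0.8, 1 gives 0.000001, 0.00079, 0.0076, 0.0244, 0.0500, as in the five-look table.

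Each table is right on its own terms. The question is the passage from one to the other.

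**2. Nominal error of the combined plan.** Under the null the Z statistics are jointly normal with correlation √(n_j/n_k). First-crossing probabilities come from recursive numerical integration.

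| Limits applied | n=50/100/150/200/224 | Equal fifths |
|---|---|---|
| Five-look limits at every look | 4.7% | 5.0% |
| Looks 1–2 three-look, looks 3–5 from addendum | 5.28% | 5.59% |
| Looks 1–3 three-look, looks 4–5 from addendum | 7.30% | 7.64% |

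Increments in the first column:

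- Second row: 0.00021 + 0.01189 + 0.00405 + 0.01515 + 0.02149 = 0.0528.
- Third row: 0.00021 + 0.01189 + 0.03791 + 0.00668 + 0.01632 = 0.0730.

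**3. Conditional error at look 2.** The documents give only 88 analysed in total, so 44 per arm is an assumption. Then Z = (0.13 − 0.12)/√(0.125 × 0.875 × 2/44) = 0.14. From there, the chance of a false positive is about 0.0007 under the three-look plan (one remaining test at 1.993, n=150). Under the addendum (2.680, 2.290 and 2.031 at 150, 200 and 224) it is about 0.0070.

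**4. The planned primary test.** IV.E item c specifies Fisher's exact test. An exact two-binomial calculation at 25/50/75/100/112 per arm, with 12.5% mortality in both arms, compares Fisher p-values with the nominal limits. For the three rows above it gives 2.9%, 3.1% and 4.3%. At 26% mortality it gives 3.3%, 3.6% and 5.0% (0.0497).

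**5. Remaining limits after two looks at 3.710 and 2.511.**

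- Keep 2.680 and 2.290: 0.0313 is used by n=200. A final value of 2.067 (two-sided p 0.0388) adds 0.0187, for a total of 0.0500.
- Or spend by A(t) at the real fractions: A(150/224) = 0.0123, A(200/224) = 0.0354, A(1) = 0.0500. This gives limits of about 3.40, 2.20 and 2.09. These rounded values total 4.98%.

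**6. Power.** Take the effect for which the addendum's table has 80% power at its own times (expected final Z 2.836). At the real sample sizes, with two old looks, power is 80.1% with a final limit of 2.031, 79.3% with 2.067, and 79.1% with 3.40/2.20/2.09.

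**The case against.** **The limits actually used are not recorded.** No section says which critical value applied at any completed look, and the current text says five analyses were planned. If the five-look limits applied throughout, nominal error is 5.0% or less and nothing is lost. This stands. Three-look limits at looks 1 and 2 are an inference. It is a strong one, because look 2 is described as two thirds of 150 and IV.D.4 still counts three analyses.

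**A reader might infer that the full 5% was already spent at n=150.** The statement that three looks have occurred invites this, but the documents do not support it. The addendum uses first- and second-look data only, shows no result at n=150, and still calls 150 the current sample size. The 7.3% figure therefore stays conditional.

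**A reader might also infer that the mortality test exceeds 5%.** The calculations do not show this. Fisher's test is conservative at these event rates and stays below 5% in every case computed. That protection is incidental. It does not cover admission INR, TEG G, base deficit and lactate, which use linear regression under the same interim rules. It may also be lost if imbalance moves the primary analysis to logistic regression (IV.D.2).

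**The consequence is modest.** With two old looks the nominal excess is 0.3 to 0.6 percentage points. IV.I.1 concedes low power and also accepts consistent trends at p 0.05 to 0.10 as promising. This limits the severity but does not make the printed 0.050 correct.

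**Conclusion.** The point holds as an undocumented transition between two designs, not as an arithmetic slip within either table. The addendum carries forward no alpha from completed looks, and the documents leave open how many were held and against which limits.

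If looks 1 and 2 were on the three-look limits, nominal two-sided error is about 5.3% at the stated sample sizes and 5.6% on equal fifths. About 7.3% (7.6%) applies only if a third look was also judged at 1.993. These are Z-scale figures. They bear mainly on the linear-regression secondary endpoints and on any adjusted primary analysis; they do not show that Fisher's test on mortality exceeds 5%. The tenfold rise in conditional error also depends on the assumed 44 per arm. Should be fixed.

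**What to change.** State in IV.D.5 and in the addendum how many looks were held, at what n, and the limit used at each. Reconcile the two-look and three-look statements, and bring IV.D.4 into line. Then recompute the remaining limits from the unspent alpha at the real information fractions (50/224, 100/224, 150/224, 200/224, 1), not 0.2 to 1.0.

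- **Two looks held on the three-look limits:** keep 2.680 and 2.290 and set the final value to about 2.07 (p about 0.039) in place of 2.031 (p 0.042), or use about 3.40, 2.20 and 2.09.
- **Look at n=150 also held at 1.993:** treat it as the confirmatory analysis and label the extension supportive.
- **Five-look limits used throughout:** say so; the printed limits can stand.

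The cost is wording, one new table and, with two looks on the old limits, about one point of power. No more patients are needed.
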